14.0 Risks and Benefits

14.1 Risks of Harm:

Identify all research-related risks of harm to which the subject will be exposed for each research procedure or intervention as a result of participation in this study. Consider the risks of breach of confidentiality, psychological, legal, social, and economic risks as well as physical risks. Do not describe risks from standard care procedures; only describe risks from procedures done for research purposes

The risks listed below are inherent in cataract surgery, the use of a toric intraocular lens, and the use of a capsular tension device.

More common and not serious::

- Blurry vision
- Photosensitivity (light sensitivity)
- Posterior capsular opacity

Less common and more serious:

- Intraocular inflammation
- Elevated intraocular pressure
- Capsular tears
- Iris tears or atrophy
- Intraocular floppy iris syndrome (IFIS)
- Vitreous problems
- Floaters
- Dropped lens
- Decentered intraocular lens
- Cortical remnants
- Optic atrophy
- Deposits on intraocular lens
- Posterior synechiae
- Glaucoma
- Iridodonesis
- Phacodonesis
- Corneal edema
- Fibrin in pupil
- Cystoid macular edema (retinal swelling)
- Need for additional surgery
- Aphakia
- Retinal tears or detachment
- Loss of vision
- Anterior vitrectomy
- Dropped lens
- Rotated lens
- Need for spectacle correction
- Astigmatism
- Accidental breach of confidentiality.

A specific risk inherent to the capsular tension ring device is that it is also possible that the capsular tension ring could be placed incorrectly into the wrong part of the eye (sulcus or anterior chamber), which may lead to damage to the surrounding structures.

14.2

Measures to Minimize Risks of Harm (Precautions, safeguards):

For each research procedure or intervention, describe all measures to minimize and/or eliminate risk of harms to subjects and study personnel

The treatment intervention involves placement of a capsular tension ring. Risks will be minimized by the surgeons being experienced with capsular tension ring placement and techniques. Risks will also be minimized by excluding patients with any conditions such as pseudoexfoliation, capsular tears, or other surgical complications. If at any time one of the patients experiences a complication, the surgeon will address it surgically or during the postoperative period, depending on the treatment required.

If at any time the patient reports a side effect, they will be referred to one of the Investigators for care.

14.3

Confidentiality Protections (for research records, data and/or specimens):

Describe in detail the plan to maintain confidentiality of the research data, specimens, and records throughout the study and at its conclusion (e.g., destruction, long term storage, or banking). Explain the plan for securing the data (e.g., use of passwords, encryption, secure servers, firewalls, and other appropriate methods). If data will be shared electronically with other team members/collaborators outside the institution, describe the method of transmission and safeguards to maintain confidentiality. Explain whether this study may collect information that State or Federal law requires to be reported to other officials or ethically requires action, e.g., child or spouse abuse

During the study, the Informed Consents, HIPAA Authorization Documents, source documents, participant registration documents, identifiable Master Key, and any other study documents utilized during the study will be stored in a locked cabinet or electronically on a CAC-enabled government computer and password protected.

Medical records will be annotated with ICD-10 code Z00.6 to reflect the subjects' participation in a research study, in which they are receiving a research-related treatment intervention.

Long-term storage: When the IRB Study Closure Letter has been obtained from the IRB, the Informed Consents, HIPAA Authorization Documents, source documents, participant registration documents, identifiable Master Key, and any other study documents utilized during the study will be scanned into a CAC-enabled government computer and electronically maintained for a minimum of 6 years.

For subjects who consent to have their coded research data placed in the "Mike O'Callaghan Military Medical Center General Research Data Repository" (FWH20180064E), the coded data will be retained for future use. The coded research data will not be utilized for further research activity beyond the protocol stipulations without additional IRB approval.

14.4 Potential Benefits:

Describe any real and potential benefits of the research to the subject and any potential benefits to a specific community or society

If the individuals in the research are considered experimental subjects (per 10 USC 980), and they cannot provide their own consent, the protocol must describe the intent to directly benefit all subjects

Eyes treated with capsular tension rings may experience less risk of the toric lens rotating out of its intended alignment. This would lead to an improvement in refractive outcome and may reduce their dependence on glasses postoperatively. They may also have a reduced risk of undergoing a second surgery to adjust the position of the toric intraocular lens. None of these benefits are guaranteed.

14.5 Privacy for Subjects:

Describe the measures to protect subject's privacy during recruitment, the consent process, and all research activities, etc.

During the study, the research consents, HIPAA Authorization Documents, participant registration forms, identifiable Master Key, and any other study documents utilized during the study will be stored in a locked cabinet or electronically on a CAC-enabled government computer and password protected.

14.6 Incidental or Unexpected Findings:

Describe the plan to address incidental findings and unexpected findings about individuals from screening to the end of the subject's participation in the research. In cases where the subject could possibly benefit medically or otherwise from the information, state whether or not the results of screening, research participation, research tests, etc., will be shared with subjects or their primary care provider. State whether the researcher is obligated or mandated to report results to appropriate military or civilian authorities and explain the potential impact on the subject

If significant new findings develop during the course of this study that may relate to subjects' decision to continue to participate in the study, they will be informed and/or their PCM will be notified.

15.0 Study Monitoring

15.1 Your study requires either Data and Safety Monitoring Plan (DSMP) or a Data and Safety Monitoring Board (DSMB).

- DSMP
- DSMB
- Both
- Not Applicable

16.0 Reportable Events

16.1 Reportable Events: Consult with the research office at your institution to ensure requirements are met. Describe plans for reporting unexpected adverse events and unanticipated problems. Address how unexpected adverse events will be identified, who will report, how often adverse events and unanticipated problems will be reviewed to determine if any changes to the protocol or consent form are needed and the scale that will be used to grade the severity of the adverse event.

Consult with the research office at your institution to ensure requirements are met

- Describe plans for reporting expected adverse events. Identify what the expected adverse events will be for this study, describe the likelihood (frequency, severity, reversibility, short-term management and any long-term implications of each expected event)
- Describe plans for reporting unexpected adverse events and unanticipated problems. Address how unexpected adverse events will be identified, who will report, how often adverse events and unanticipated problems will be reviewed to determine if any changes to the research protocol or consent form are needed and the scale that will be used to grade the severity of the adverse event

A. Adverse Events (AEs) are defined as "any untoward medical or surgical occurrence in the study eye, which does not necessarily have a causal relationship with the trial intervention." AEs will be assessed at all visits and during the surgical procedure. AEs will be assessed using all available clinical modalities, including but not limited to: patient history, slit lamp examination, intra-operative observation, and ancillary clinical testing such as Optical Coherence Tomography (OCT), visual corneal topography, refraction, etc.

B. All AEs and Unanticipated Adverse Effects will be documented and records maintained, regardless of whether thought to be device-related, procedure/operation-related, or not.

C. Adverse Event: The investigator(s) on this protocol will complete an Adverse Event Reporting Form (also referred to as a Case Report Form) for each AE. The form will be reviewed by the Research Monitor and submitted to the governing IRB and FDA as consistent with all required policies.

D. Serious Adverse Event: An adverse event where the outcome is one of the following:

-Death

- Life-threatening, where the patient was at substantial risk of dying or continued use of the product might have resulted in death
- Hospitalization or prolongation of an existing hospitalization
- Disability or permanent damage, interfering with the patient's ability to conduct normal life functions
- Congenital anomaly or birth defect
- Required intervention to prevent permanent impairment

E. Unanticipated Adverse Device Effect: An effect not outlined in study documents or an event that occurs more often than expected. Required policies as outlined in 21 CFR 812.150 (a1) (b) involve submitting unanticipated adverse device effects to the FDA and IRB, with investigators required to submit the unanticipated ADE report less than or equal to working days of their own notification. Investigators may be required by the FDA to submit follow-up reports regarding an UADE. In the case of this proposed study, "The Investigation of Capsular Tension Rings in Intraocular Lens Rotation," the sponsor is the investigator, eliminating one of the reporting steps. An AE may be reclassified as an UADE in the event the effect is revealed to be more frequent than expected.

F. Descriptions and Definitions of AEs:

- Relationship to device: definite, probably, possible, unlikely, etc.
- Relationship of event to implantation procedure or operation: definite, probably, possible, unlikely, etc.
- Severity of the event: mild, moderate, severe, vision-threatening, lifethreatening, etc.
- Subsequent treatments or interventions required: none, medical therapy, surgical or procedural intervention, hospitalization, etc.
- Resolution status: resolved without sequelae, resolved with chronic sequelae, ongoing without sequelae, ongoing with sequelae, etc.

Withdrawal of subjects due to adverse events: Patients will be discontinued from the study if any intraoperative complications or adverse events are noted prior to capsular tension ring insertion. Intraoperative complications may include capsular bag tears or rents, anterior vitrectomy, phacodonesis, damaged zonules, use of non-toric lens, or other intraoperative complications that would influence capsular bag or lens positioning or stability.

If intraoperative complications or adverse events occur after the point of possible capsular tension ring insertion, the patient will continue to be enrolled in the study to further characterize the safety of the investigational device and treatment. Complete and thorough pre-, intra-, and post-operative care will be provided for all patients regardless of enrollment status in the study. All patients, including patients who experience an adverse event, will continue in the study and receive appropriate treatment and/or monitoring throughout the duration required based on their clinical needs, regardless of whether the study eye is discontinued or an adverse event occurs.

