12.0 Participant Information

12.1 Subject Population:

Active duty and DoD beneficiaries aged 30 years or older undergoing cataract surgery. Patients who are pregnant or lactating will be excluded because the risks of surgery and post-operative medication to the unborn fetus are unknown. Patients under 30 years of age will not be included because they are likely to have congenital, pediatric, or juvenile-onset cataracts, which is outside the scope of this study. Corneal astigmatism ≥ 1.0 D and a surgical plan that includes a toric intraocular lens for astigmatism correction.

12.2 Age Range:

Check all the boxes that apply. If the age range of potential subjects (specimens, records) does not match the range(s) selected, please specify in the text box.

- 0-17
- 18-24
- 25-34
- 35-44

45-54
 55-64
 65-74
 75+

12.3 Gender:

Male
 Female
 Other

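### Serious events that do not arise in a study eye have no adverse-event reporting route unless they count as unanticipated effects, although the serious-event list is largely patient-level (sections 16.1 and 18.4)

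*Combined protocol and SAP*

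**What the plan says.** Section 16.1, item A, defines an AE as "any untoward medical or surgical occurrence in the study eye, which does not necessarily have a causal relationship with the trial intervention". AEs are assessed during surgery and at every visit. Item D then introduces the serious category: "Serious Adverse Event: An adverse event where the outcome is one of the following". Six outcomes follow: death; a threat to life, worded as "Life-threatening, where the patient was at substantial risk of dying or continued use of the product might have resulted in death"; a stay in hospital, worded as "Hospitalization or prolongation of an existing hospitalization"; lasting disability or damage; "Congenital anomaly or birth defect"; and intervention required to prevent permanent impairment.

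Item B requires records of all AEs and unanticipated adverse effects, whatever their presumed cause. Item C requires a form for each AE, review by the Research Monitor, and submission to the IRB and FDA under the applicable policies. Item E defines an unanticipated adverse device effect as "An effect not outlined in study documents or an event that occurs more often than expected", with no restriction to the eye. Item F grades AEs for relation to the device and to the procedure, severity, consequences and resolution.

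Section 18.4 repeats these definitions (items 1 and 4 match items A and D), so the eye-only wording is not a slip in one place.

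**The concern.** The two definitions do not fit together. The SAE list is written about the patient, but the AE definition that it depends on is written about one organ. Item A deliberately sets causality aside, yet an event is screened out by its location before anyone grades whether the device or the operation caused it.

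This is a significant-risk device study under an investigational device exemption. Section 13.6 keeps subjects enrolled after complications at or after the point of ring insertion in order to describe safety further. A hospitalization for a systemic reaction on the day of surgery is something such a study would want on record and graded for relation to the procedure. Under the definitions as written, the site could correctly complete no AE form for it.

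**Working it through.** No arithmetic tests the definitions themselves. The check sets them side by side and runs each kind of serious event through them.

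**Step 1: the nesting.** By item A, an AE is an occurrence in a study eye. By item D, an SAE is "An adverse event where the outcome is one of the following". So every SAE must be a study-eye occurrence. Neither section gives a separate SAE route; the form, monitor review and submission in item C attach to AEs.

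**Step 2: the cases.**

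| Serious event with a listed outcome | AE? | SAE? | Other stated route |
|---|---|---|---|
| Arises in a study eye and leads to death, a life-threatening state or hospitalization | Yes | Yes | Not needed |
| Arises in a fellow eye that is also enrolled | Yes, it is a study eye | Yes | Not needed |
| Arises in a fellow eye that is not enrolled | No | No | Item E only, if it qualifies |
| Systemic, linked to device or surgery, not described in study documents | No | No | Arguably item E |
| Systemic, unrelated or already expected | No | No | None |
| Birth defect | No | No, although listed | Item E only, if it qualifies |

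The first row follows because item D tests the outcome, not where the outcome is felt. Item F confirms it: it allows an AE to be life-threatening or to lead to hospitalization. The second row follows from section 10.1, under which a fellow eye that meets the criteria is enrolled too. In the last row, a birth defect cannot realistically be the outcome of an occurrence in the participant's eye, so that list item is effectively empty.

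**Step 3: how far item E helps.** It has two limbs. The first covers effects not described in the study documents. The risk list in section 14.1 names no death, cardiac event or drug reaction, so a systemic event linked to surgery could be argued in. The second covers events more frequent than expected. Item E describes this as reclassifying an AE, and a frequency cannot be judged for events that were never logged as AEs.

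**Step 4: how many eyes are concerned.** Section 11.2 plans 50 eyes. If u subjects enroll one eye and b enroll both, then u + 2b = 50. The number of subjects, u + b, lies between 25 (all enroll both: u = 0, b = 25) and 50 (all enroll one: u = 50, b = 0). The number of non-enrolled fellow eyes is u, so it lies between 0 and 50. The systemic gap applies to every subject in either case.

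**The case against.** The strongest reply is that the plan has other safeguards. Item E is not limited to the eye and goes to the FDA and IRB. The Research Monitor works full-time at the site, oversees patients before, during and after surgery, and reviews the data collection (section 5.2). An eye-only scope may also be a deliberate choice for an ocular device. Finally, pregnant and lactating patients are excluded and pregnancy during the study is a ground for withdrawal, so the birth-defect item has little practical reach.

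Much of this stands and limits the point. Item E catches some systemic events, and the monitor may learn of others informally. The statement in section 12.1 that "the risks of surgery and post-operative medication to the unborn fetus are unknown" explains an exclusion; it is not a risk accepted for enrolled subjects and then left unrecorded. Eye-only recording is also reasonable for minor events.

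What does not stand is that these safeguards close the gap. Item E does not cover expected or unrelated systemic serious events. A monitor's general oversight is not a stated duty to record or submit. A deliberate eye-only scope would not explain a patient-level SAE list beneath it.

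A reader might infer more: that no death or hospitalization could ever count as serious, that the safety record would show none by construction, or that all fellow-eye events are lost. The documents do not support this. Study-eye events with those outcomes qualify, and an enrolled fellow eye is itself a study eye. Nor does the number of patient-level items on the list measure the share of safety data lost.

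**Conclusion.** The point holds in limited form. Sections 16.1 and 18.4 contradict their own SAE list. Serious events that do not arise in a study eye, and are not unanticipated effects, have no stated AE or SAE form, monitor review, or IRB and FDA route. The events concerned are systemic deaths, life-threatening events and hospitalizations, birth defects, and serious events in a non-enrolled fellow eye.

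The documents give no rates for such events, so the expected number cannot be stated. What can be stated is the exposure: 25 to 50 subjects for systemic events, and 0 to 50 non-enrolled fellow eyes, followed to the month-6 visit (up to 210 days after surgery). The conclusion assumes that the site applies the definitions literally and that no other study procedure, outside these documents, collects systemic SAEs.

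This should be corrected because it concerns the safety record of a significant-risk device. It does not touch the rotation endpoint, its analysis or the stated power.

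**What to change.** Reconcile the two definitions in both places: section 16.1 items A and D, and section 18.4 items 1 and 4.

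- Define an SAE as any untoward medical occurrence in an enrolled subject, in any location, that has one of the outcomes already listed. Use the period in which AEs are already assessed: during surgery and at all visits.
- State that item C (form, Research Monitor review, and submission under the applicable policies) applies to these SAEs as well as to AEs.
- Leave non-serious AE recording limited to the study eye, if the sponsor prefers.
- Record the location of each event: study eye (with its arm), fellow eye, or systemic. The form is not in the documents and may already have such a field.
- Report eye-located events by arm and systemic SAEs by subject. Because eyes are randomized independently, a subject with two enrolled eyes may be in both arms, so a systemic event cannot always be assigned to one.

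The cost is a short change of wording in two sections, at most one field on the form, and a few more forms for unrelated systemic serious events. No visit is added, because patient history is already part of the AE assessment at each visit.

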17.0 Equipment/non-FDA Regulated Devices

17.1 Does the study involve the use of any unique non-medical devices/equipment?

Yes No

18.0 FDA-Regulated Products

18.1 Will any drugs, dietary supplements, biologics, or devices be utilized in this study?

- Drugs
- Dietary Supplements
- Biologics
- Devices
- N/A

18.3 Device Details:

Are device(s) in this research being used in accordance to the approved labeling?
 Are device(s) in this research being used in a manner other than its approved labeling?

When adding a device indicate in the details section of the device if the use is either used in accordance to the approved labeling or in a manner other than its approved labeling

View Details	Device Name
⊕	MORCHER® capsular tension ring
Manufacturer/Supplier of Device	MORCHER® EYEJET® CTR Types 14, 14A, and 14C
Where will the Devices Be Stored	stored separately from clinic stock and labeled in accordance with FDA Investigational Device Exemption (IDE# G190139)
Will Devices be supplied at no Cost	Yes
Is this a HDE (HDE)	No
HDE Number	
Who holds the IDE	N/A
IDE details	FDA approved Investigational Device Exemption (IDE# G190139)

18.4 Reporting Requirements for FDA-regulated research under IND and IDE:

Describe the process for complying with FDA regulatory requirements for adverse event reporting and adverse device effects reporting to the sponsor

1. Adverse Events (AEs) are defined as "any untoward medical or surgical occurrence in the study eye, which does not necessarily have a causal relationship with the trial intervention." AEs will be assessed at all visits and during the surgical procedure. AEs will be assessed using all available clinical modalities, including but not limited to: patient history, slit lamp examination, intra-operative observation, and ancillary clinical testing such as Optical Coherence Tomography (OCT), visual corneal topography, refraction, etc.
2. All AEs and Unanticipated Adverse Effects will be documented and records maintained, regardless of whether thought to be device-related, procedure/operation-related, or not.
3. Adverse Event: The investigator(s) on this protocol will complete an Adverse Event Reporting Form (also referred to as a Case Report Form) for each AE. The form will be reviewed by the Research Monitor and submitted to the governing IRB and FDA as consistent with all required policies.
4. Serious Adverse Event: An adverse event where the outcome is one of the following:
 1. Death
 2. Life-threatening, where the patient was at substantial risk of dying or continued use of the product might have resulted in death
 3. Hospitalization or prolongation of an existing hospitalization
 4. Disability or permanent damage, interfering with the patient's ability to conduct normal life functions
 5. Congenital anomaly or birth defect
 6. Required intervention to prevent permanent impairment
5. Unanticipated Adverse Device Effect: An effect not outlined in study documents or an event that occurs more often than expected. Required policies as outlined in 21 CFR 812.150 (a1) (b) involve submitting unanticipated adverse device effects to the FDA and IRB, with investigators required to submit the unanticipated ADE report less than or equal to 10 working days of their own notification. Investigators may be required by the FDA to submit follow-up reports regarding an UADE. In the case of this proposed study, "The Investigation of Capsular Tension Rings in Intraocular Lens Rotation," the sponsor is the investigator, eliminating one of the reporting steps. An AE may be reclassified as an UADE in the event the effect is revealed to be more frequent than expected.
6. Descriptions and Definitions of AEs:

- a. Relationship to device: definite, probably, possible, unlikely, etc.
- b. Relationship of event to implantation procedure or operation: definite, probably, possible, unlikely, etc.
- c. Severity of the event: mild, moderate, severe, vision-threatening, life-threatening, etc.
- d. Subsequent treatments or interventions required: none, medical therapy, surgical or procedural intervention, hospitalization, etc.

Resolution status: resolved without sequelae, resolved with chronic sequelae, ongoing without sequelae, ongoing with sequelae, etc.

18.5 Sponsor (organization/institution/company):

N/A

If applicable, provide sponsor contact information:

